6.5.4.1 Liver Safety Assessment

The following potentially clinically significant criteria in liver function tests for Alkaline Phosphatase (ALP), Alanine Transaminase (ALT), total bilirubin, Aspartate Transaminase (AST) and their combination are defined. The participant's highest value during the investigational period will be used.

Parameter	Criteria
ALT	> 3xULN > 5xULN > 10xULN > 20xULN
AST	> 3xULN > 5xULN > 10xULN > 20xULN
ALT or AST	> 3xULN > 5xULN > 10xULN > 20xULN
Total Bilirubin	> 2xULN
ALP	> 1.5xULN
ALT and/or AST AND Total Bilirubin ^(*)	(ALT and/or AST > 3xULN) and (Total bilirubin > 2xULN)
ALT and/or AST AND Total Bilirubin AND ALP ^(*)	(ALT and/or AST > 3xULN) and Total bilirubin > 2xULN and ALP < 2xULN

(*) Combination of values measured within same sample

The number and percentage of participants with potentially clinically significant values in liver enzymes and total bilirubin during the investigational period will be presented by dose level, phase, tumor type, and overall.

6.5.5 Vital Signs

The baseline value is the last measurement taken prior to the first study drug administration.

Vital signs (systolic blood pressure [SBP], diastolic blood pressure [DBP], pulse rate, respiratory rate, body temperature and weight) will be summarized using mean, standard deviation, minimum, maximum and median by dose level, phase, tumor type, and overall. Additionally, a within-participant change will be calculated per visit as the post-baseline measurement minus the baseline measurement and summarized by visit. Within-participant change will also be calculated from pre-dose and reported.

Tables for potentially clinically significant vital signs will be generated using baseline value and highest post-baseline value for each participant.

The following criteria are defined as clinically significant for each parameter:

Vital Sign Variable	Criteria
SBP	≥ 180 mmHg AND ≥ 20 mmHg change from baseline
DBP	≥ 105 mmHg AND ≥ 15 mmHg change from baseline
Pulse Rate	≥ 120 bpm AND ≥ 15 bpm change from baseline

Vital signs data will be displayed in listings.

6.5.6 Electrocardiograms (ECGs)

The three values of each ECG parameter within a time point from the central reviewer will be averaged to determine time-specific parameter for a participant, and used in summaries.

ECG variables will be summarized using mean, standard deviation, minimum, maximum and median for each dose level, phase, tumor type, and overall at each treatment visit and time point, including changes from baseline.

Number and percentage of participants with normal and abnormal results as assessed by central review for the overall interpretation will be tabulated by dose level, phase, tumor type, and overall at each treatment visit and time point. A shift analysis table showing shift in overall ECG interpretation from baseline to each time point will be provided. The worst of the three overall ECG interpretations will be used as the time-specific overall ECG interpretation for a participant.

The QT interval corrected for heart rate by Fridericia's formula, QTcF, is defined as: $QTc(F) = QT/(RR)^{0.33}$, where RR interval is inversely proportional to heart rate (approximately RR = 60/heart rate).

The QTcF interval will be summarized using frequency tables for each treatment visit and time point for values of clinical importance using the range criteria below.

	QTc Interval Criteria Value (msec)	
	Cumulative Category	Interval Category
Normal	≤ 450	≤ 450
Borderline	> 450	> 450 to ≤ 480
Prolonged	> 480	> 480 to ≤ 500
Clinically significant	> 500	> 500

The QTcF interval will also be summarized by the frequencies of participants with a change from baseline of clinical importance using the criteria identified below. These summaries will be provided for each treatment visit and time point.

Variable	Change from Baseline	
	Cumulative Category	Interval Category
QTc Interval (msec)	<0	<0
	≥ 0	≥ 0 to ≤ 30
	> 30	> 30 to ≤ 60
	> 60	> 60

Number and percent of participants with 12 lead ECG abnormalities as well as number and percent of participants whose 12 lead ECG reading changed from normal at baseline to abnormal will be tabulated by dose level, phase, tumor type, and overall at each treatment visit and time point.

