5.2.1.8 Electrocardiogram (ECG)

12-lead ECGs will be recorded in triplicate at the scheduled time points. Each ECG tracing will be taken 2 minutes apart. ECGs will be read at the site for clinical decision making and transmitted to a central reviewer. Data from the central reviewer will be used in summary presentations.

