6.9 Additional Conventions

6.9.1 Analysis Windows

No visit window will be used; nominal visit date will be considered date of visit.

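### SAP 6.5.6 tabulates QTcF outliers only by visit and time point, so no planned table counts the participants who ever exceeded 500 ms or ever rose by more than 60 ms

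*SAP*

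**What the plan says.** SAP 6.5.6 plans two sets of QTcF categories. The first classifies the value itself, with thresholds at 450, 480 and 500 ms; the SAP labels the top category clinically significant. On layout it says "The QTcF interval will be summarized using frequency tables for each treatment visit and time point for values of clinical importance". The second classifies the change from baseline, with thresholds at 0, 30 and 60 ms, and again "These summaries will be provided for each treatment visit and time point".

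The value that enters these tables is a mean: "The three values of each ECG parameter within a time point from the central reviewer will be averaged to determine time-specific parameter". The only worst-value rule in the section is "The worst of the three overall ECG interpretations will be used as the time-specific overall ECG interpretation for a participant". It works within one time point and concerns the overall reading, not QTcF.

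On data source, SAP 5.2.1.8 says "12-lead ECGs will be recorded in triplicate at the scheduled time points" and "Data from the central reviewer will be used in summary presentations". SAP 6.9.1 adds "No visit window will be used; nominal visit date will be considered date of visit".

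Other safety domains are treated differently. SAP 6.5.5 says "Tables for potentially clinically significant vital signs will be generated using baseline value and highest post-baseline value for each participant". SAP 6.5.4.1 uses each participant's highest liver test value, and SAP 6.5.4 includes a shift from baseline to the worst post-baseline laboratory grade.

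**The concern.** ECGs are named in the primary safety endpoint (protocol Table 8, SAP 2.1). The natural summary question is how many participants ever reached a QTcF that the SAP itself calls clinically significant, and how many ever rose by more than 60 ms. A set of tables by visit does not answer it. Isolated excursions in different people at different visits are spread over many tables, and one person's repeated excursions look the same in the margins as single excursions in several people.

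What is at stake is whether the study report can state a participant-level incidence of QTcF prolongation from a planned table. Without one, that number must be assembled by hand or added after the data are seen.

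**Working it through.** **1. Is a participant-level maximum defined anywhere?** No. Both QTcF category sets in SAP 6.5.6 are by treatment visit and time point, as are the tabulations of abnormal ECGs and of changes from normal to abnormal. The columns headed as cumulative use nested thresholds (above 450, above 480, above 500 ms); they do not accumulate over visits. Protocol 9.4.3.4.1 also summarizes by time point. It adds a listing of interpretations and quantitative values, which SAP 6.5.6 does not repeat.

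**2. How many time points does the information spread over?** The inputs are protocol Table 2 and its footnote h, for monotherapy expansion and a participant completing six cycles. The Cycle 1 Day 1 pre-dose ECG serves as baseline.
- Cycle 1 Day 1 post-dose: 1
- Day 1 of Cycles 2 to 6, pre- and post-dose: 5 × 2 = 10
- EOT: 1

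This gives k = 12. If the EOT ECG falls after ASP7517 has stopped and is therefore single and locally read, k = 11 for centrally read data.

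**3. What do by-visit proportions say about the ever-affected proportion?** The documents give no QTcF event rate, so there is no planned figure to reproduce and every rate below is assumed. Let each time point show proportion p above the threshold, with everyone present.
- Lower bound (the same people each time): p
- Upper bound (different people each time): min(1, k × p)
- Independence between time points: 1 − (1 − p)^k

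Take one participant at each time point in a cohort of 43, the monotherapy maximum in protocol 4.1.6.1. Each table shows 1/43 = 2.3%. With k = 12, the ever-affected share lies between 1/43 = 2.3% and 12/43 = 27.9%. With k = 11, the upper end is 11/43 = 25.6%.

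Other assumed rates, with k = 12:

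| p per time point | Same people | Independence | Different people |
|---|---|---|---|
| 0.5% | 0.5% | 5.8% | 6% |
| 1% | 1% | 11.4% | 12% |
| 2% | 2% | 21.5% | 24% |

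**4. In which direction can a by-visit figure mislead?** A by-visit count can never exceed the ever-affected count. A percentage can fall on either side. Two assumed examples use the stage 1 size of 18:
- Three participants each exceed 500 ms once, at three different visits with all 18 present. Each of those tables shows 1/18 = 5.6%, while 3/18 = 16.7% were affected.
- Only five participants remain at Cycle 6, and one of them is the only person ever above 500 ms. The Cycle 6 table shows 1/5 = 20%, while 1/18 = 5.6% were affected.

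**The case against.** The strongest reply is that prolongation is not hidden.
- The by-visit summaries include the maximum, so any scheduled triplicate mean above 500 ms is visible.
- The protocol promises a listing of quantitative ECG values, from which a reader could count.
- ECG abnormalities judged clinically significant and not due to the underlying disease are reported as adverse events (protocol 10.3.1 and 10.3.1.1), and the TEAE tables count each participant once per preferred term (SAP 6.5.2).
- The study closed early and the analyses were deliberately reduced (SAP 5.1.1 and section 7), so cohorts of 18 or 43 may not exist, and in small groups a listing goes a long way.
- Worst-value tables are not a general principle of this SAP: ECOG status is summarized by visit too (SAP 6.5.8).

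All of this is fair, and it keeps the point small. It does not fill the gap. A by-visit maximum shows that an excursion occurred, not how many different people had one. A listing is not a planned count. The adverse event route depends on investigator judgement rather than the SAP's QTcF thresholds.

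A reader might also infer more than the documents support:
- **That unscheduled ECGs are excluded.** The SAP does not say how they are handled. Their absence from the tables is a reasonable inference from scheduled recording, by-visit layout and no visit windows, but SAP 6.9.1 does not state it, and SAP 6.9.4, on outliers, says that all values enter the analyses.
- **That every by-visit table understates the incidence, or that a maximum row can only raise the reported rate.** This is true of counts but not of percentages, as the Cycle 6 example shows.

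**Conclusion.** The point holds as a gap in reporting. The SAP plans no participant-level count of QTcF above 500 ms or of an increase above 60 ms, although it uses highest or worst values for liver tests, vital signs and laboratory grade shifts and gives no reason for treating QTcF differently. By-visit margins leave the ever-affected share open over a wide range: 2.3% to 27.9% in the illustration with 43 participants and 12 time points.

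The size rests on assumed excursion rates, full cohorts and complete attendance; the trial's own figures could be zero. The structural conclusion, that these tables cannot yield the participant count, needs none of those assumptions. The documents do not support the stronger readings that prolongation is concealed, that incidence is always understated, or that unscheduled ECGs are known to drop out. Sample size, type I error and power are unaffected. This is a cheap improvement, not a flaw that threatens the trial's conclusions.

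**What to change.** In SAP 6.5.6, add a maximum post-baseline row to both QTcF tables, counting each participant once:
- **Value:** the largest centrally read time-point mean QTcF and, for the change table, the largest increase from baseline. Take both over all centrally read post-baseline ECGs, scheduled or unscheduled, and say so explicitly.
- **Denominator:** participants with a baseline and at least one post-baseline ECG, held fixed.
- **Other ECG sources:** in expansion, ECGs after ASP7517 stops are single (triplicate if deemed necessary) and locally read (protocol Table 2 footnote h and 7.2.4). Show the single, locally read ones separately or flagged, because SAP 5.2.1.8 bases summaries on central readings and a maximum that mixes the two sources would be noisier.
- **Role:** report this row as the main QTcF outlier result and keep the by-visit tables as support.

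The cost is one derived record per participant and a short rule on ECG source. No new data are needed. The count in the new row will be at least as large as any by-visit count based on the same ECGs; its percentage may be higher or lower than a given by-visit percentage.

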6.5.7 Pregnancies

A detailed listing of all pregnancies will be provided.

6.5.8 Eastern Cooperative Oncology Group (ECOG) Performance Status

Number and percent of participants for each category of the ECOG performance status at each assessment time will be provided. The change from baseline to EOT score will also be summarized. Negative change scores indicate an improvement. Positive change scores indicate a decline in performance.

ECOG will also be summarized using shift table from baseline to post-baseline score for each dose level, phase, tumor type, and overall by visit.

6.6 Analysis of Pharmacokinetics

Cellular DNA load and kinetic parameters of ASP7517, as well as serum concentration of pembrolizumab will be summarized by using descriptive statistics including n, mean, standard deviation, minimum, median, maximum, coefficient of variation (CV), geometric mean, and geometric CV. Spaghetti and mean time-course of cellular DNA load will be constructed.

6.6.1 Estimation of Pharmacokinetic Parameters

Participants with sufficient cellular DNA samples will have kinetic parameter estimates for ASP7517 including calculation of AUC, C_{max} , and t_{max} . for each cycle estimated by the pharmacokineticist using a non-compartmental analysis method in reference to Manual for Non-Compartmental Analysis of Pharmacokinetic Data from Studies using PhoenixTM® WinNonlin® (Certara, Saint Louis, Missouri, US) software version 6.4 or higher.

Exploratory analysis between pharmacokinetic parameters and clinical measures (e.g., efficacy or safety) may be performed.

6.7 Analysis of Exploratory Endpoints

Biomarkers/Pharmacodynamics

Immune cell phenotyping biomarkers will be summarized by change from baseline at each time point by both absolute number and percentage.

6.8 Interim Analysis (and Early Discontinuation of the Clinical Study)

No interim analysis to be performed.

6.9 Additional Conventions

6.9.1 Analysis Windows

No visit window will be used; nominal visit date will be considered date of visit.

6.9.2 Imputation Rules for Incomplete Dates

Missing or partial start and stop dates of adverse events, concomitant medications, and new anti-cancer therapy will be imputed according to Astellas standards using the following algorithm:

- Imputation rules for partial or missing stop dates:
 - If the month and year are present, then impute as the last day of that month.
 - If only the year is present, impute as December 31 of that year.
 - If the stop date is entirely missing, assume the event or medication is ongoing.
- Imputation rules for partial or missing start dates:

Start Date		Stop Date						missing	
		Complete: yyyymmdd		Partial: yyyyymm		Partial: yyyy			
		< 1 st dose	≥ 1 st dose	< 1 st dose yyyyymm	≥ 1 st dose yyyyymm	< 1 st dose yyyy	≥ 1 st dose yyyy		
Partial: yyyymm	= 1 st dose yyyymm	2	1	2	1	n/a	1	1	
	≠ 1 st dose yyyymm		2		2	2	2	2	
Partial: yyyy	= 1 st dose yyyy	3	1	3	1	n/a	1	1	
	≠ 1 st dose yyyy		3		3	3	3	3	
Missing		4	1	4	1	4	1	1	

1 = Impute as the date of first dose; 2 = Impute as the first of the month; 3 = Impute as January 1 of the year;
4 = Impute as January 1 of the stop year

For survival and other time-to-event endpoints, missing or incomplete death date will be imputed as the earliest feasible date on or after the date last known to be alive as the examples shown in the table below.

Incomplete date of death or new anti-cancer therapy	Date Last Known to be Alive/Not Started New Treatment	Imputed Date
?? APR 2020	31 MAR 2020	01 APR 2020
14 ??? 2020	31 MAR 2020	14 APR 2020
?? ??? 2020	31 MAR 2020	31 MAR 2020
?? APR ????	31 MAR 2020	01 APR 2020
14 APR ????	31 MAR 2020	14 APR 2020
?? ??? ????	31 MAR 2020	31 MAR 2020

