5.1.2.6 Progression-free Survival per RECIST v1.1 (PFS)

PFS is defined as the time from the start of the study treatment until death from any cause or radiographic disease progression assessed per RECIST v1.1 by investigator assessment, whichever occurs first.

Table 3 PFS Definition

PFS		
Situation	Date of Event or Censor	Outcome
No evaluable post-baseline imaging assessments, no death	Date of first dose (Day 1)	Censor
Participant did not receive new anti-cancer therapy:		
Radiographical progression documented per RECIST v1.1	Date of radiological disease progression	Event

PFS		
Situation	Date of Event or Censor	Outcome
No radiographical progression, but death recorded on eCRF	Date of death	Event
Neither radiographical progression nor death	Date of last disease assessment	Censor
Participant received new anti-cancer (ACT) therapy:		
Radiographical progression documented per RECIST v1.1 after new ACT	Date of last radiological assessment before start of new anti-cancer therapy	Censor
Radiographical progression documented per RECIST v1.1 before new ACT	Date of radiological disease progression	Event
No radiographical progression before new ACT but death recorded	Date of last radiological assessment before start of new anti-cancer therapy	Censor
No radiographical disease progression nor death	Date of last radiological assessment before start of new anti-cancer therapy	Censor
Missed >=2 scheduled radiological assessments		
If radiographical progression or death occurs after missing 2 scheduled radiological assessments	Date of last radiological assessment before missing 2 scans	Censor

PFS = Date of Event or Censor – Date of First Dose +1

Missing 2 scheduled imaging assessments:

Missing 2 scheduled imaging assessments is defined as the gap between two imaging assessments being more than 140 days (2.5 times the scheduled imaging assessment interval (2.5 x 56 days)). Imaging assessments after first iUPD will be excluded in PFS derivation.

Note: Participant cannot be censored at “NE”. If NE is the only previous assessment, then PFS will be censored at Day 1.

To apply the cut-off date to PFS is to exclude those tumor assessments after cut-off date and anti-cancer therapy date after cut-off date in the analysis.

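### SAP 6.9.2 gives two conflicting imputation rules for the start of new anti-cancer therapy and no precedence; following the general one can turn a documented progression into a censoring

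*SAP*

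**What the plan says.** SAP Section 6.9.2 handles incomplete dates in two parts.

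The first part is a general algorithm: "Missing or partial start and stop dates of adverse events, concomitant medications, and new anti-cancer therapy will be imputed". Its start-date grid uses four codes, the first being "1 = Impute as the date of first dose". With the stop date missing, or on or after first dose, code 1 applies to a wholly missing start and to a partial start matching the month or year of first dose. A start known to another month becomes the first of that month; a start known only to another year becomes 1 January of that year. For stop dates, "If the stop date is entirely missing, assume the event or medication is ongoing".

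The second part is introduced for survival and other time-to-event endpoints. Its sentence says that a "missing or incomplete death date will be imputed as the earliest feasible date on or after the date last known to be alive". The table beneath it is wider than the sentence: one column is headed "Incomplete date of death or new anti-cancer therapy" and the anchor column "Date Last Known to be Alive/Not Started New Treatment".

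The date matters because of the censoring tables. In SAP Table 3 (Section 5.1.2.6), the case "Radiographical progression documented per RECIST v1.1 after new ACT" is a censoring, dated "Date of last radiological assessment before start of new anti-cancer therapy". Tables 2, 4 and 5 (iPFS, iDOR, DOR) depend on the therapy start in the same way.

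**The concern.** One variable falls under two rules that give different answers, and the text does not say which prevails. Setting an unknown start to the first dose is cautious for adverse events, because it errs towards calling an event treatment-emergent. For a date that ends follow-up it works the other way: everything seen after first dose, including a documented progression, then falls after new therapy.

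The imputed value is also implausible for this variable. Protocol Section 6.8 prohibits other anticancer therapy during treatment, and the end-of-treatment footnotes to Protocol Tables 1 and 2 require that visit before new therapy starts. A new therapy dated to the first dose contradicts the design.

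At stake are the Kaplan-Meier summaries of PFS and iPFS (SAP Sections 6.4.2.5 and 6.4.2.6) and the listed values of DOR and iDOR. The loss would not be neutral: where the participants affected have documented progression, removing their events tends to make PFS look longer.

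**Working it through.** **1. The plan's own figures.** The second table works six examples with the anchor at 31 Mar 2020. Applying its rule (the earliest calendar date on or after the anchor that agrees with the known parts) gives 1 Apr, 14 Apr, 31 Mar, 1 Apr, 14 Apr and 31 Mar 2020. All six match the SAP.

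**2. The conflict in one of those examples.** For a date known only as 2020, the second table gives 31 Mar 2020. For a new therapy start, the grid gives the date of first dose for anyone first dosed in 2020, if the stop date is missing or not before first dose.

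**3. Effect on PFS.** Inputs, chosen for illustration: first dose 10 Feb 2022; first post-baseline scan, showing progression, 6 Apr 2022; last known not on new therapy 20 Apr 2022 (assumed); stop date missing. The formula in SAP Table 3 is event or censoring date minus first dose date plus 1. From 10 Feb to 6 Apr is 28 + 27 = 55 days, so progression is on Day 56, within the protocol's 56 ± 7 day scan schedule.

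| Therapy start as recorded | Grid | PFS by grid | Second table | PFS by second table |
|---|---|---|---|---|
| Missing | 10 Feb 2022 (code 1) | Censored, event lost | 20 Apr 2022 | Event, Day 56 |
| 2022 | 10 Feb 2022 (code 1) | Censored, event lost | 20 Apr 2022 | Event, Day 56 |
| Apr 2022 | 1 Apr 2022 (code 2) | Censored, event lost | 20 Apr 2022 | Event, Day 56 |

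**4. Where the censoring falls.** No post-baseline scan precedes the grid's date in any of these rows. The natural fallback is Day 1. Read literally, the last scan before therapy is the screening scan. If that scan was k days before first dose, PFS is 1 − k; with k from 1 to 28 (the screening window) this runs from 0 to −27. Either way the event is lost and no follow-up is counted.

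**5. A later progression, month known.** First dose 15 Jan 2020, clear scan on Day 57 (11 Mar), progression on Day 113 (6 May), last known untreated 20 May (assumed), therapy start recorded as May 2020. The grid gives 1 May 2020, so PFS is censored at Day 57. The second table gives 20 May 2020, so PFS is an event at Day 113.

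**6. Duration of response.** For a responder whose therapy start is set to the first dose, the last scan before therapy precedes the response itself, so the censoring date falls before the start of the duration being measured.

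**The case against.** The best defence is that the second rule was written for exactly this purpose. It is introduced for time-to-event endpoints, its table heading names new therapy, and its anchor column refers to treatment not yet started, which has little use except for censoring. A specific rule normally displaces a general one, and the grid keeps a role for stop dates and listings. For participants who follow the protocol, the end-of-treatment visit precedes new therapy, so a usable anchor should exist. Most of this stands: the second table is probably what was intended. It does not close the gap, because the introductory sentence covers only death dates while the grid names new therapy without restriction. A programmer could follow either.

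A reader might infer that the SAP as written censors at Day 1 every participant whose therapy date is missing or known only to the year of first dose. The documents do not support that. It happens only if the grid is chosen. Day 1 is also inferred: the Day 1 row of Table 3 is for participants with no evaluable post-baseline imaging, and these participants have a scan.

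Nor does the second table rescue every case as it stands. If the anchor is the progression date itself, a missing or year-only start is imputed to that same day, and Table 3 has rows only for progression before or after new therapy. The tie is unresolved. The example above avoids it by assuming a later anchor.

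**Conclusion.** The conflict is real and should be settled. Where the grid is followed, a documented progression can be lost from PFS or iPFS, as the Day 56 and Day 113 examples show. The examples rest on assumed dates, a missing stop date and an anchor 14 days after progression.

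The overall size cannot be stated, because the documents give no frequency of incomplete therapy dates. The reach is limited. These are secondary, descriptive endpoints; after early closure DOR and iDOR are only listed (SAP Sections 6.4.2.7 and 6.4.2.8); and nothing shows that iORR depends on this date. A reader might go further and conclude that the PFS results are wrong. That does not follow, since the rule probably intended gives the right answer apart from ties.

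**What to change.** In SAP Section 6.9.2:

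- Exclude start dates of new anti-cancer therapy from the general grid, but keep its stop-date rule for that therapy. Striking the therapy from the opening sentence altogether would leave its stop dates with no rule, because the second table imputes a single date only.
- Widen the sentence above the second table so that it covers the start of new therapy as well as death, anchored on the date last known alive or last known not to have started new treatment, as applicable.
- State that this rule alone supplies the therapy start used in PFS, iPFS, DOR and iDOR.
- State that progression on the same date as an imputed therapy start counts as occurring before it.

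The cost is SAP wording and a check that the derivation programs follow it. No new data are needed. If the SAP is already final, the rule applied should be documented in the clinical study report, as SAP Section 1 provides for changes to the planned analyses.
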